## 2 PROTOCOL SYNOPSIS

**Title** A Phase 3 Study Evaluating the Pharmacokinetics, Safety, and Tolerability of VX-445/TEZ/IVA Triple Combination Therapy in Cystic Fibrosis Subjects 6 Through 11 Years of Age

**Brief Title** Evaluation of VX-445/TEZ/IVA in Cystic Fibrosis Subjects 6 Through 11 Years

**Clinical Phase and Clinical Study Type** Phase 3, pharmacokinetics (PK), safety, and tolerability

**Objectives** **Part A**

Primary Objective

To evaluate the PK of VX-445, tezacaftor (TEZ), and ivacaftor (IVA) when dosed in triple combination (TC)

Secondary Objectives

- To evaluate the PK of VX-445, TEZ and IVA metabolites
- To evaluate the safety and tolerability of VX-445/TEZ/IVA

**Part B**

Primary Objective

To evaluate the safety and tolerability of VX-445/TEZ/IVA through Week 24

Secondary Objectives

- To evaluate the efficacy of VX-445/TEZ/IVA through Week 24
- To evaluate the PK of VX-445, TEZ, and IVA
- To evaluate the PK of VX-445, TEZ and IVA metabolites

**Endpoints** **Part A**

Primary Endpoint

PK parameters of VX-445, TEZ, and IVA, including  $C_{max}$ ,  $C_{trough}$ , and  $AUC_{0-\tau}$

Secondary Endpoints

- PK parameters of VX-445, TEZ, and IVA metabolites, including  $C_{max}$ ,  $C_{trough}$ , and  $AUC_{0-\tau}$
- Safety and tolerability as determined by adverse events (AEs), clinical laboratory values, standard 12-lead ECGs, vital signs, and pulse oximetry

**Part B**

Primary Endpoint

Safety and tolerability assessments based on AEs, clinical laboratory values, standard 12-lead ECGs, vital signs, pulse oximetry, and ophthalmologic examinations

Secondary Endpoints

- Absolute change in percent predicted forced expiratory volume in 1 second (ppFEV1) from baseline through Week 24
- Absolute change in sweat chloride (SwCl) from baseline through Week 24
- Absolute change in Cystic Fibrosis Questionnaire-Revised (CFQ-R) respiratory domain score from baseline through Week 24
- Absolute change in body mass index (BMI) and BMI-for-age z-score from baseline at Week 24

- Absolute change in weight and weight-for-age z-score from baseline at Week 24
- Absolute change in height and height-for-age z-score from baseline at Week 24
- Drug acceptability assessment using Modified Facial Hedonic Scale
- Number of pulmonary exacerbations (PEx) and CF-related hospitalizations through Week 24
- PK parameters of VX-445, TEZ, IVA, and relevant metabolites
- Absolute change in lung clearance index2.5 (LCI2.5) from baseline through Week 24

Number of Subjects	
Part A Approximately 12 subjects are planned for enrollment. Subjects who participate in Part A may participate in Part B.
 
Part B Approximately 56 subjects are planned for enrollment.

Study Population	Male and female cystic fibrosis (CF) subjects 6 through 11 years of age who are homozygous for F508del (F/F genotype) or heterozygous for F508del and a minimal function (MF) mutation that is not responsive to IVA and TEZ/IVA (F/MF genotypes). Approximately 25 subjects with F/MF genotypes and approximately 20 subjects with F/F genotypes are targeted for enrollment in Part B.
Investigational Drug	
Part A Active substance: VX-445/TEZ/IVA Activity: CFTR correctors (VX-445 and TEZ) and CFTR potentiator (IVA) (increased chloride ion secretion) Strength and route of administration: 100-mg VX-445/50-mg TEZ/75-mg IVA fixed-dose combination (FDC) tablet for oral administration AND 75-mg IVA tablet for oral administration Dose administered:
 
 
• VX-445 100 mg qd/TEZ 50 mg qd/IVA 75 mg q12h; 1 × VX-445/TEZ/IVA FDC tablet in the morning and 1 × IVA tablet in the evening
 
 
Part B Active substance: VX-445/TEZ/IVA Activity: CFTR correctors (VX-445 and TEZ) and CFTR potentiator (IVA) (increased chloride ion secretion) Strength and route of administration:
 
 
• Subjects <30 kg at Day 1: 50-mg VX-445/25-mg TEZ/37.5-mg IVA FDC tablets for oral administration AND 75-mg IVA tablet for oral administration
 
• Subjects ≥30 kg at Day 1: 100-mg VX-445/50-mg TEZ/75-mg IVA FDC tablets for oral administration AND 150-mg IVA tablet for oral administration
 
 
Doses administered:
 
 
• Subjects <30 kg at Day 1: VX-445 100 mg qd/TEZ 50 mg qd/IVA 75 mg q12h
 
• Subjects ≥30 kg at Day 1: VX-445 200 mg qd/TEZ 100 mg qd/IVA 150 mg q12h
 

**Study Duration Part A**

Excluding the Screening Period, subjects will participate in the study for up to 6 weeks (± 7 days)

**Part B**

Excluding the Screening Period, subjects will participate in the study for up to 28 weeks (± 7 days)

[figure not shown]
**Study Design**

This is a Phase 3, 2-part (Parts A and B), multicenter study evaluating the PK, safety, and tolerability of VX-445/TEZ/IVA TC therapy in CF (F/F and F/MF genotypes) subjects 6 through 11 years of age (inclusive).

**Part A**

A schematic of the study design for Part A is provided below. Approximately 12 subjects (F/F or F/MF genotypes) are planned for enrollment. During the Treatment Period, subjects will be administered VX-445/TEZ/IVA for approximately 15 days. A review of safety, tolerability, and available PK data will be completed by an internal Vertex team after Part A to confirm or adjust the dose(s) chosen for Part B. Additional subjects may be enrolled as needed in Part A, based on emerging PK data, to confirm the dose(s) for Part B.

**Part A Study Design**

IVA: ivacaftor; n: number of subjects; TEZ: tezacaftor

a VX-445/TEZ/IVA will be administered from Day 1 through Day 15. On Day 15, only the morning dose will be administered.

[figure not shown]
**Part B**

A schematic of the study design for Part B is provided below. Part B will initiate after completion of the internal Vertex team’s review of available data in Part A that will confirm or adjust the dose(s) to be evaluated in Part B. Approximately 56 subjects (F/F or F/MF genotypes) are planned for enrollment to ensure approximately 45 subjects complete Part B. Approximately 25 subjects with F/MF genotypes and approximately 20 subjects with F/F genotypes are targeted for enrollment in Part B. During the Treatment Period, subjects will be administered VX-445/TEZ/IVA for approximately 24 weeks.

Subjects who complete the Part B Treatment Period and have not permanently discontinued study drug will be offered the opportunity to enroll in an optional open-label extension safety study (enrollment will be based on the eligibility criteria specified within the Open-label Extension Safety Study protocol).

**Part B Study Design**

IVA: ivacaftor; TEZ: tezacaftor

- a The Safety Follow-up Visit is scheduled to occur 4 weeks ( $\pm$  7 days) after the last dose. This visit is not required for subjects who enroll in an optional open-label extension safety study within 28 days of the last dose.
- b Subjects who complete the visits in the Treatment Period, regardless of whether they are on a treatment interruption, will be offered the opportunity to enroll in an optional open-label extension safety study evaluating VX-445 in a triple combination regimen.

**Parts A and B Doses**

Subject Weight at Day 1	VX-445 Dose	TEZ Dose	IVA Dose
Part A			
All weights	100 mg qd	50 mg qd	75 mg q12h
Part B			
<30 kg	100 mg qd	50 mg qd	75 mg q12h
$\geq$ 30 kg	200 mg qd	100 mg qd	150 mg q12h

IVA: ivacaftor; qd: once daily; q12h: every 12 hours; TEZ: tezacaftor

**Assessments Parts A and B**

**PK Assessments:**

PK parameters for VX-445, M23-445, TEZ, M1-TEZ, IVA, M1-IVA

**Safety Assessments:**

AEs, clinical laboratory assessments (serum chemistry, hematology, coagulation, and urinalysis), standard 12-lead ECGs, vital signs, pulse oximetry, ophthalmologic examinations, and physical examinations (PEs)

**Efficacy Assessments:**

Spirometry and sweat chloride

**Part B**

**Efficacy Assessments:**

Weight, height, BMI, CFQ-R, multiple-breath washout (MBW), and other events related to outcome (e.g., PEX)

**Other Assessments:**

- Drug acceptability assessment using Modified Facial Hedonic Scale.

**Statistical** Data from Parts A and Part B will be analyzed separately.

**Analyses**

**Part A**

Approximately 12 subjects will be enrolled in Part A. Sample size calculations were determined based on VX-445 PK using noncompartmental analysis-based parameters, such as clearance and volume of distribution. Based on the variability observed in adults, data from 12 subjects will allow 80% power to target a 95% CI within 60% and 140% of the geometric mean estimate of clearance for VX-445.

**Part B**

With 45 subjects expected to complete Part B, there is a 90% chance of observing an AE in at least 1 subject if the true incidence rate is 5%, and a >95% chance of observing an AE in at least 1 subject if the true incidence rate is 10%.

For the primary endpoint, summary statistics will be provided for treatment-emergent AEs, clinical laboratory assessments, standard 12-lead ECGs, vital signs, and pulse oximetry.

**IDMC Reviews** An independent data monitoring committee (IDMC) will conduct periodic safety review(s) of study data as outlined in the IDMC charter (Part B only).

### 3 SCHEDULE OF ASSESSMENTS

The schedules of assessments are shown in Table 3-1 (Part A Screening Period), Table 3-2 (Part A Treatment Period and Safety Follow-up Visit), Table 3-3 (Part B Screening Period), and Table 3-4 (Part B Treatment Period and Safety Follow-up Visit).

**Table 3-1 VX18-445-106, Part A Screening Period**

Assessment	Screening Visit (Day -28 to Day -1)	Comments
Informed Consent (and Assent)	X	
Demographics	X	Section 11.1 for details
Medical History	X	Section 11.1 for details
Ophthalmologic Examination	X	Conducted by an ophthalmologist or optometrist (Section 11.5.5)
Full Physical Examination	X	Section 11.5.3 for details
Weight, Height, and BMI	X	Weight and height will be measured with shoes off (Section 11.4.4)
Vital Signs	X	Collected after the subject has been at rest for at least 5 minutes (Section 11.5.3)
Pulse Oximetry	X	Collected after the subject has been at rest for at least 5 minutes (Section 11.5.3)
Standard 12-lead ECG	X	Performed after the subject has been at rest for at least 5 minutes (Section 11.5.4)
Spirometry	X	Performed pre- or post-bronchodilator (Section 11.4.1). Screening spirometry evaluation may be repeated, as specified in (Section 9.1.1.1).
Sweat chloride	X	Section 11.4.2 for details
CF Genotype (all subjects)	X	If the CFTR genotype result is not received before the first dose of study drug, a previous CFTR genotype laboratory report may be used to establish eligibility (Section 8.1). Subjects who have been enrolled whose screening genotype does not confirm study eligibility must be discontinued from the study (Section 9.9).
Serum Pregnancy Test (females of childbearing potential)	X	Females of childbearing potential is defined as females 10 years of age and older (Section 11.5.6)
Serum Chemistry	X	Section 11.5.2 for details
Hematology	X	Section 11.5.2 for details
Coagulation Studies	X	Section 11.5.2 for details
G6PD Activity Test	X	Section 11.5.2 for details
Urinalysis	X	Section 11.5.2 for details
Drug Test (urine only)	X	Section 11.5.2 for details
Alcohol Test (urine only)	X	Section 11.5.2 for details
Inclusion/Exclusion Criteria Review	X	Section 8 for details
Medication Review	X	
AEs and SAEs	X	Continuous, From Signing of ICF (and Assent Form)

**Table 3-2 VX18-445-106, Part A Treatment Period and Safety Follow-up Visit**

Assessment a	Day 1	Day 2	Day 4 (± 1 Day)	Day 8 (± 1 Day)	Day 15 (± 1 Day)	ETT Visit	Safety Follow-up Visit 28 (± 7) Days After the Last Dose of Study Drug	Comments
Clinic Visit	X	X		X	X	X	X	
Telephone Contact			X					
Inclusion and Exclusion Criteria Review	X							Section 8 for details
Safety Assessments								
Full Physical Examination	X				X	X	X	Section 11.5.3 for details. Symptom-directed physical examinations will occur at any time during the study if deemed necessary by the investigator.
Weight, Height, and BMI	X				X	X	X	Weight and height will be measured before study drug dosing with shoes off (Section 11.4.4).
Vital Signs	X	X		X	X	X	X	Collected after the subject has been at rest for at least 5 minutes (Section 11.5.3)
Pulse Oximetry	X	X		X	X	X	X	Collected after the subject has been at rest for at least 5 minutes (Section 11.5.3)
Standard 12-lead ECG	X (triplicate)	X			X	X	X	Day 1 and 2: before the AM dose Day 15: before the AM dose and 4 hours (+/- 30 min) after the AM dose Performed after the subject has been at rest for at least 5 minutes (Section 11.5.4)
Spirometry	X	X		X	X	X	X	Should be performed pre-bronchodilator, before the AM dose, and at approximately the same time at each visit (Section 11.4.1).
Sweat chloride	X				X			Collection will be done approximately at the same time as predose blood collections; however they may not be done at exactly the same time (Section 11.4.2).
Pregnancy Test (females of childbearing potential)	X (urine)				X (urine)	X (urine)	X (urine)	Females of childbearing potential is defined as females 10 years of age and older (Section 11.5.6)
Serum Chemistry	X			X	X	X	X	Section 11.5.2 for details
Hematology	X			X	X	X	X	Section 11.5.2 for details.
Coagulation	X				X			Section 11.5.2 for details.
Drug Test (urine)	X							Section 11.5.2 for details.
Alcohol Test (urine)	X							Section 11.5.2 for details.

a All assessments will be performed before study drug dosing (within 60 minutes) unless noted otherwise (Section 11).

**Table 3-2 VX18-445-106, Part A Treatment Period and Safety Follow-up Visit**

Assessment a	Day 1	Day 2	Day 4 (± 1 Day)	Day 8 (± 1 Day)	Day 15 (± 1 Day)	ETT Visit	Safety Follow-up Visit 28 (± 7) Days After the Last Dose of Study Drug	Comments
Observation 4 hours After the Morning Dose	X							
Concomitant Medications	Continuous, From Signing of ICF (and Assent Form) Through Completion of Study Participation							
Concomitant Treatments and Procedures	Continuous, From Signing of ICF (and Assent Form) Through Completion of Study Participation							
AEs and SAEs	Continuous, From Signing of ICF (and Assent Form) Through Completion of Study Participation							
PK Assessments								
PK Sampling	X			X	X			
Day 1: before the AM dose, and at 1, 2, 4, and 6 hours after the AM dose
 
Day 8: before the AM dose
 
Day 15: before the AM dose, and at 1, 2, 4, and 6 hours after the AM dose
 
If study drug is not administered on the day of the visit (i.e., study drug interruption or permanent discontinuation of study drug), only 1 PK blood sample will be collected.
 
See Table 11-1 for details.

Study Drug Administration								
Meal(s) or Snack(s) at Site	X	X		X	X			
Fat-containing food such as a standard “CF” meal or snack will be provided at the site to subjects after all predose assessments have occurred.
 
Section 9.6.1 for details.

VX-445/TEZ/IVA	
Day 1 Through Day 15 (morning dose only on Day 15)
 
Administered within approximately 30 minutes of consuming fat-containing food (e.g., standard “CF” meal or snack) (Section 9.6.1). On scheduled visits, the AM dose of study drug will be administered at the site after predose assessments have been completed (food to be provided by site on these days).
							

**Table 3-3 VX18-445-106, Part B Screening Period**

Assessment	Screening Visit (Day -28 to Day -1)	Comments
Informed Consent (and Assent)	X	
Demographics	X	Section 11.1 for details
Medical History	X	Section 11.1 for details
Ophthalmologic Examination	X	Conducted by an ophthalmologist or optometrist (Section 11.5.5)
Full Physical Examination	X	Section 11.5.3 for details
Weight, Height, and BMI	X	Weight and height will be measured with shoes off (Section 11.4.4).
Vital Signs	X	Collected after the subject has been at rest for at least 5 minutes (Section 11.5.3)
Pulse Oximetry	X	Collected after the subject has been at rest for at least 5 minutes (Section 11.5.3)
Standard 12-lead ECG	X	Performed after the subject has been at rest for at least 5 minutes (Section 11.5.4)
Multiple-breath Washout	X	Performed in multiple replicates pre- or post-bronchodilator and before the spirometry assessment (Section 11.4.3)
Spirometry	X	Performed pre- or post-bronchodilator (Section 11.4.1). Screening spirometry evaluation may be repeated, as specified in (Section 9.1.1.1).
Sweat Chloride	X	Section 11.4.2 for details
CF Genotype (all subjects)	X	If the CFTR genotype result is not received before the first dose of study drug, a previous CFTR genotype laboratory report may be used to establish eligibility (Section 8.1). Subjects who have been enrolled whose screening genotype does not confirm study eligibility must be discontinued from the study (Section 9.9).
Serum Pregnancy Test (all female subjects)	X	Section 11.5.2 for details
Serum Chemistry	X	Section 11.5.2 for details
Hematology	X	Section 11.5.2 for details
Coagulation	X	Section 11.5.2 for details
Urinalysis	X	Section 11.5.2 for details
Inclusion/Exclusion Criteria Review	X	Section 8 for details
Medication Review	X	Information regarding medications taken within 56 days before the Screening Visit will be collected (Section 9.5)
AEs and SAEs	X	Continuous, From Signing of ICF (and Assent Form)

**Table 3-4 VX18-445-106, Part B Treatment Period and Safety Follow-up Visit**

Event/ Assessment a	Day 1	Day 3 (± 1 day)	Day 15 (± 3 days)	Week 4 (± 5 days)	Week 8 (± 5 days)	Week 12 (± 5 days)	Week 16 (± 5 days)	Week 20 (± 5 days)	Week 24 (± 5 days)	ETT Visit	Safety Follow-up Visit 28 (± 7) Days After the Last Dose of Study Drug b	Comments
Clinic Visit	X		X	X	X	X	X		X	X	X	
Telephone Contact		X						X				Assess the subject's status, any AEs, concomitant medications, treatments, and procedures.
Inclusion and Exclusion Criteria Review	X											Section 8 for details
Safety and Efficacy Assessments												
CFQ-R	X			X	X	X	X		X	X	X	Completed before the start of any other assessments (Section 11.4.5).
Modified Facial Hedonic Scale	X		X	X	X	X	X		X	X	X	Completed immediately after dosing with study drug (Section 11.3.1).
Ophthalmologic Examination									X at or up to 4 weeks before	X		Section 11.5.5
Full Physical Examination	X					X			X	X		Section 11.5.3 for details. Symptom-directed physical examinations will occur at any time during the study if deemed necessary by the investigator.
Weight, Height, and BMI	X		X	X	X	X	X		X	X	X	Weight and height will be measured before study drug dosing with shoes off (Section 11.4.4).
Vital Signs	X		X	X	X	X	X		X	X	X	Collected after the subject has been at rest for at least 5 minutes (Section 11.5.3)

a All assessments will be performed before study drug dosing unless noted otherwise (Section 11). For any assessments with multiple time points for an individual visit, only 1 set of assessments will be collected if study drug is not administered on the day of the visit (i.e., study drug interruption or permanent discontinuation of study drug).

b The Safety Follow-up Visit is not required for subjects who complete the Week 24 Visit and enroll in the optional open-label extension safety study within 28 days after the last dose.

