**Table 3-4 VX18-445-106, Part B Treatment Period and Safety Follow-up Visit**

Event/ Assessment a	Day 1	Day 3 (± 1 day)	Day 15 (± 3 days)	Week 4 (± 5 days)	Week 8 (± 5 days)	Week 12 (± 5 days)	Week 16 (± 5 days)	Week 20 (± 5 days)	Week 24 (± 5 days)	ETT Visit	Safety Follow-up Visit 28 (± 7) Days After the Last Dose of Study Drug b	Comments
PK Assessments												
Single PK Sampling			X			X			X			Blood samples collected before dosing must be collected within 60 minutes before dosing. See Table 11-1 for details.
Serial PK Sampling	X											Day 1: Blood samples collected at 2, 4, and 6 hours after the AM dose. Week 4: Blood samples collected before dosing (within 60 minutes before dosing) and 1, 2, 4, and 6 hours after the AM dose. If study drug is not administered on the day of the visit (i.e., study drug interruption or permanent discontinuation of study drug), only 1 PK blood sample will be collected. See Table 11-1 for details.
Study Drug Administration												
VX-445/TEZ/IVA	VX-445/TEZ/IVA (Day 1 through evening before Week 24 Visit)											Administered within approximately 30 minutes of consuming fat-containing food (e.g., standard “CF” meal or snack) (Section 9.6.1). On scheduled visits, the AM dose of study drug will be administered at the site after

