#### Part B

The Safety Follow-up Visit is scheduled to occur 28 ( $\pm$  7) days after the last dose of study drug for subjects who complete study drug dosing and for subjects who prematurely discontinue study drug dosing, as described in Section 9.1.4.

An optional open-label extension safety study will be available for subjects who complete the last treatment period visit and are eligible. The Safety Follow-up Visit is not required for subjects who complete the Week 24 Visit and enroll in the optional open-label extension safety study within 28 days after the last dose of study drug.

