#### Part B

If the ETT Visit occurs 3 weeks or later following the last dose of study drug, then the ETT Visit will replace the Safety Follow-up Visit, and a separate Safety Follow-up Visit will not be required.

Subjects who prematurely discontinue study drug treatment will continue to complete all scheduled study visits for assessments following completion of the ETT Visit, as detailed in [Table 3-4](#).

Subjects who prematurely discontinue treatment in Part B are not eligible to enroll in the optional open-label extension safety study.

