**Table 9-3 Study Drug Administration, Part B**

Subject Weight at Day 1	Tablet Strength	Time	Number of Tablets Taken
<30 kg	50-mg VX-445/25-mg TEZ/37.5-mg IVA	AM	2 tablets
	75-mg IVA	PM	1 tablet
≥30 kg	100-mg VX-445/50-mg TEZ/75-mg IVA	AM	2 tablets
	150-mg IVA	PM	1 tablet

IVA: ivacaftor; TEZ: tezacaftor

Study drug should be administered with a fat-containing meal or snack, such as a standard “CF” meal or snack or a standard meal according to the following guidelines:

1. It is recommended that the dose be taken within 30 minutes of the start of the meal or snack.
2. All doses of study drug (morning and evening, as applicable) should be administered at approximately every 12 hours ( $\pm$  2 hours) on each dosing occasion (e.g., if the morning doses of study drug are administered at 08:00 hour on Day 1, all subsequent morning doses should be administered between 06:00 hour and 10:00 hour).
3. At the Day 1 Visit, all subjects will be observed for 4 hours after the morning dose of the study drug.
4. The date, amount taken, and time of study drug administration including whether food was taken with each dose, will be recorded for 2 days before PK sample collection and on the days of PK sample collection.
5. On days of scheduled visits (Day 1, Day 15, Weeks 4, 8, 12, and 16), the morning dose of study drug will be administered at the site after predose assessments have been completed. The meal or snack will be provided by the site for the morning dose of study drug.
6. For visits after the Day 1 Visit, subjects will be instructed to bring all used and unused study drug to the site; study drug will be dispensed at each visit, as appropriate.
7. At the Week 24 Visit, the morning dose of study drug will NOT be administered. The last dose of study drug will be the evening dose administered the day before the Week 24 Visit.

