## **11.3.1 Modified Facial Hedonic Scale for Drug Acceptability Assessment**

### **Part B**

The acceptability of study drug will be assessed by the investigator and authorized designee. All subjects will be observed for their facial expressions and the reaction will be scored using a visual analog scale; any spontaneous comments in regards to likes or dislikes will also be noted. Interviews will be conducted on a one-on-one basis in the clinic setting. The Modified Facial

Hedonic Scale questionnaire for drug acceptability will be completed immediately after dosing with study drug.

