9.3.2 Efficacy Analysis for Part B

There is no multiplicity adjustment; *P*-values provided for the secondary and other endpoints in Part B are considered nominal.

All efficacy analyses described in this section will be based on the FAS, unless otherwise specified. The analysis will include all available measurements through the last scheduled visit, including measurements after treatment discontinuation.

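### The drug-acceptability scale must follow a dose, yet it is scheduled and analysed at Week 24 and Safety Follow-up, where none is given, and the SAP does not apply the post-dose rule

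*Protocol*

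**What the plan says.** Drug acceptability on the Modified Facial Hedonic Scale is a Part B secondary endpoint (Protocol Section 7.2). Its timing is set twice, without exception. The comment in the scale's row of Protocol Table 3-4 reads "Completed immediately after dosing with study drug (Section 11.3.1", and Section 11.3.1 says that the scale's "questionnaire for drug acceptability will be completed immediately after dosing with study drug". Section 11.3.1 has the child's facial reaction observed and scored, with interviews held in the clinic. Section 9.3.4 adds that the caregiver's view of convenience, ease of administration and the child's acceptance is also evaluated.

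Table 3-4 marks the scale at nine visits: Day 1, Day 15, Weeks 4, 8, 12, 16 and 24, ETT and Safety Follow-up.

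On dosing, item 5 of Protocol Section 9.6.1 (Part B) has the dose taken on site and names the visits concerned: "On days of scheduled visits (Day 1, Day 15, Weeks 4, 8, 12, and 16), the morning dose of study drug will be administered". Item 7 states: "At the Week 24 Visit, the morning dose of study drug will NOT be administered". The drug row of Table 3-4 agrees: "VX-445/TEZ/IVA (Day 1 through evening before Week 24 Visit". Section 9.1.3 sets the Safety Follow-up Visit at 28 days, with a margin of 7 either way, in these words: "days after the last dose of study drug for subjects who complete study drug dosing and for subjects who prematurely discontinue study drug dosing".

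SAP Section 9.3.2.2.1 defines the scale only by reference to Protocol Section 11.3.1. SAP Section 9.3.2.2.2 summarises each question at all scheduled visits; its only inclusion rule specific to the scale is clinic versus home. SAP Section 9.3.2 adds: "The analysis will include all available measurements through the last scheduled visit, including measurements after treatment discontinuation". SAP Table 12-2 gives the scale eight windows, including Week 24 and Safety Follow-up.

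**The concern.** An instruction to complete a form straight after a dose cannot be followed at a visit without one. The documents leave two outcomes open. Sites may complete the form anyway, and responses given without a dose are then tabulated as acceptability of study drug. Or sites may apply the timing rule literally, and the Week 24 and Safety Follow-up rows of the clinic-based table are empty or nearly so. The SAP does not say which to expect or how to treat an undosed form.

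The gap also reaches earlier rows. Section 9.1.4 (Part B) says: "Subjects who prematurely discontinue study drug treatment will continue to complete all scheduled study visits for assessments following completion of the ETT Visit". A child who has stopped drug can therefore contribute forms to rows that otherwise hold post-dose reactions, and nothing in the table would show it. The same applies to a child on a temporary interruption. What is at stake is the meaning of one descriptive endpoint.

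**Working it through.** The plan states no figure to reproduce. The check sets the schedule against the dosing rules and then follows the forms through the SAP windows.

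**Step 1. Visits against doses** (Protocol Table 3-4, Sections 9.1.3 and 9.6.1; SAP Table 12-2)

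| Visit | Scale marked | Dose at visit | Own row in SAP Table 12-2 |
|---|---|---|---|
| Day 1 | yes | yes | yes |
| Day 15 | yes | yes | yes |
| Week 4 | yes | yes | yes |
| Week 8 | yes | yes | yes |
| Week 12 | yes | yes | yes |
| Week 16 | yes | yes | yes |
| Week 24 | yes | no | yes |
| ETT | yes | not stated | no |
| Safety Follow-up | yes | no | yes |

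Of 9 marked visits, 6 have a site dose, 2 have none and 1 is not stated (6 + 2 + 1 = 9). Of 8 analysis rows, 2 have no scheduled dose: 2/8 = 25%.

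**Step 2. Per completer.** A child who enters the extension study within 28 days needs no Safety Follow-up Visit and has 7 scheduled forms, 1 of them undosed. A child who does not enter it has 8, 2 of them undosed.

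**Step 3. Do the undosed forms reach the tables?**
- Week 24 is Day 169 ± 5, so Day 164 to 174. That lies inside the scale's Week 24 window (141, 183].
- The last dose is the evening before, so Day 163 to 173.
- Safety Follow-up is then Day 163 + 21 = 184 at the earliest and Day 173 + 35 = 208 at the latest. The scale's Safety Follow-up window is >183.

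Both forms therefore fall in their own rows when the visits keep to schedule.

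**Step 4. Earlier rows.** Two hypothetical children show how undosed forms enter them.
- Last dose on Day 30: Safety Follow-up is Day 51 to 65, inside the Week 8 window (43, 71]. The Week 8 visit itself, still attended, is also undosed.
- Week 8 visit on Day 52 with a dose, drug then stopped, ETT on Day 56 (assumed undosed): the distances from target Day 57 are 5 and 1 days. Note 2 to SAP Table 12-2 selects the closer form, so the undosed one replaces the dosed one.

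The number of such children cannot be derived from the documents.

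**The case against.** Several points can be made for the plan.

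- *The SAP imports the rule by citing Section 11.3.1.* This is true of the definition. But no inclusion, windowing or selection rule uses it, and the general rule that keeps data after discontinuation works against it.
- *Dose-relative comments are used loosely in Table 3-4.* ECG and spirometry are to precede the morning dose, yet both are marked at Week 24 and Safety Follow-up. That does no harm, because an instruction to measure before a dose is still met when none follows. An instruction to measure after a dose is not.
- *Footnote a to Table 3-4 covers visits without study drug.* It deals with assessments that have several time points at one visit. The scale has one.
- *The drug row's comment has the morning dose given at the site on scheduled visits.* The row itself ends the evening before Week 24, and Section 9.6.1 item 7 excludes that visit expressly.
- *Not every item needs a dose minutes earlier.* This stands. Caregiver views on convenience and ease of administration (Section 9.3.4) can reasonably be recalled at Week 24, after about 24 weeks of use. A reader might infer that every undosed form is worthless as acceptability data. The documents do not support that; the problem is clearest for the child's immediate reaction.
- *Post-dose data after Week 16 are possible.* This also stands. SAP Section 4 foresees scales completed at home, and Section 9.3.2.2.2 allows an optional analysis of clinic and home data together. Unscheduled visits are windowed too, and the Week 24 window opens after Day 141, while children are still on daily drug. A reader might infer that no post-dose figure can exist after Week 16. That holds only for the scheduled clinic visits.

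**Conclusion.** The inconsistency is real. The scale's row in Table 3-4 cannot be followed together with the drug row at Week 24, or with the timing of Safety Follow-up, and the SAP carries the conflict into its tables. By schedule, 2 of 8 analysis rows have no clinic dose to react to. This counts Week 24 and Safety Follow-up only and assumes visits run as planned; ETT remains open because the documents do not state whether a dose is given.

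The number of undosed forms in the earlier rows is unknown. A reader might take the planned shortfall, 56 − 45 = 11 children, as an upper limit. It is not one: it counts children expected not to complete Part B, not those who stop drug and keep attending, and it leaves out temporary interruptions.

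The consequence is small. The endpoint is descriptive, no test or model uses it, and no safety result depends on it. The Day 1 to Week 16 rows of children who stay on drug do not change. The correction is worth making because it is cheap and the endpoint is named, but no main conclusion of the trial rests on it.

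**What to change.** **Protocol.** Reconcile the scale's row in Table 3-4 with the post-dose rule for Week 24, ETT and Safety Follow-up, and say for each whether the scale is collected and on what footing. This concerns collection of the scale only; dosing stays as it is.

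**SAP Section 9.3.2.2.2 and Table 12-2.**
1. Include immediate-reaction items in the acceptability summary only when the form followed a dose at that assessment, in the clinic or, for the optional analysis, at home.
2. Apply this before the closest-to-target selection, so that an undosed form cannot displace a dosed one.
3. Tabulate undosed forms separately and label them so. Caregiver convenience and ease-of-administration items may be kept there as recalled responses.

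**Cost.** The text change is one schedule row and a few lines of the SAP. Establishing dose status takes more work. Dose times are recorded only around PK sampling (Protocol Section 9.6.1, Part B, item 4), and Weeks 8 and 16 have no PK sample. Status must therefore come from the supervised site dose (Protocol Section 10.6), the last dose date and the interruption records. SAP Section 9.2.6 defines interruption by day, so an interruption of the evening dose alone would also be flagged and need checking. The documents describe no dose record for home forms, so that link would have to be captured or its absence stated.

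**Downside.** The clinic-based Week 24 row will hold few or no post-dose forms.
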